3.4.2 SECONDARY OBJECTIVES AND OUTCOMES

Our secondary objectives are to determine the effect of NAVA technology compared to conventional IMV on the following:

- All-cause mortality (2 months and 6 months from randomisation)
- Time to first extubation
- Reintubation
- Use of non-invasive ventilation following extubation
- ICU and hospital length of stay
- Serious adverse events up to hospital discharge
- HRQoL at 2 months and 6 months from randomisation
- Acute health care use at 6 months following randomisation
- Within-trial cost-utility analysis from an NHS hospital care perspective (see below)

- Safety endpoints (see also section 'Serious adverse events up to hospital discharge')
- Pre-specified complications including
 - Naso-gastric tube entering brain
 - Naso-gastric tube positioned in lungs (unrecognised/not corrected)
 - Traumatic nasogastric catheter insertion (oesophageal perforation)
 - Traumatic nasogastric catheter insertion (nasal/pharyngeal bleeding)
 - Aspiration of stomach contents
 - Pneumothorax
 - Unplanned removal of ETT or Tracheostomy
 - Unplanned removal of naso-gastric tube
 - Unplanned removal of any other invasive/indwelling device
 - Any pressure injury caused by naso-gastric catheter
 - MRI scan performed with NAVA naso-gastric catheter in situ
 - Reportable safety events that fall outside of those reported as trial outcomes

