3.9 POST-RANDOMISATION WITHDRAWALS, EXCLUSIONS AND MOVES OUT OF REGION

Participants, or their consultee on their behalf, may request to be withdrawn from the trial at any time without prejudice. Those that choose to withdraw from the trial intervention will continue to be followed-up as per the trial protocol, unless consent for this is explicitly withdrawn by the participant (or consultee if the participant lacks capacity).

In the event that a participant is transferred to another hospital, intervention delivery will usually stop at the point of transfer. The recruiting hospital will liaise with the new hospital to facilitate collection of follow-up data.

In the event that a randomised participant is later found to be ineligible, they will continue to be followed-up and will be included in study analyses.

If a NAVA catheter is replaced by a non-NAVA catheter before 28 days based on clinical grounds this will be considered an intervention withdrawal.

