4.4 INTERVENTION DURATION

The intervention (NAVA technology or control) will continue until one of the following criteria is met:

- 28 days after randomisation
- Successful unassisted breathing
- Study intervention-related serious adverse event
- Death or discontinuation of active treatment
- Person giving consent requests discontinuation of intervention
- NAVA equipment unavailable

NAVA catheters are currently licensed for a maximum of five days' use. Where it is clinically appropriate and safe, NAVA catheters should be replaced at five days. Use of individual NAVA catheters for more than 5 days is outside the trial protocol. Although this will not be reported as a protocol deviation, the clinical justification will be recorded.

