6.1 PRE-SPECIFIED COMPLICATIONS

As per the CoReCCT Safety Reporting Process (Section 7 of the CoReCCT Master Protocol), adverse events that 1) occur at sites between randomisation and hospital discharge and 2) are not present on the CoReCCT Exemption List, must be reviewed for their presence on the NAVA Pre-Specified Complications List as given below:

- Related to naso-gastric catheter placement;
 - a. Naso-gastric tube entering brain
 - b. Naso-gastric tube positioned in lungs (unrecognised/not corrected)
 - c. Traumatic nasogastric catheter insertion (oesophageal perforation)
 - d. Traumatic nasogastric catheter insertion (nasal/pharyngeal bleeding)
 - e. Aspiration of stomach contents
 - f. Pneumothorax
- Other
 - a. Unplanned removal of ETT or Tracheostomy
 - b. Unplanned removal of naso-gastric tube
 - c. Unplanned removal of any other invasive/indwelling device
 - d. Any pressure injury caused by naso-gastric catheter
 - e. MRI scan performed with NAVA naso-gastric catheter in situ (NAVA catheters are MRI unsafe due to potential harm from movement or the generation of heat in the metallic electrodes. They may also cause artifacts in the MRI images.)

The events listed above must be entered onto the eCRF when appropriate as outcomes of interest, and therefore are exempt from SAE reporting. If an event occurs which does not appear either on the

CoReCCT Exemption List or on the NAVA pre-specified complication list above, it must be assessed for seriousness, and the remainder of the CoReCCT safety reporting process should be followed to determine the next steps to be taken. Pre-specified complications will be collected onto the eCRF for the duration of the trial intervention up to 28 days. Any occurrence following this will be reported via the safety reporting process described in Section 7 of the CoReCCT Master Protocol.

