6.3 REPORTING RESPONSIBILITIES SUMMARY

All SAE/SADE/UADEs need to be reported via the CDMS to the trial team within one working day of the investigator team becoming aware of them. Reports of related and unexpected SAEs should be submitted to ethics within 15 days of the Chief Investigator becoming aware of the event.

All reporting to the sponsor should as much information about the incident as possible and should be signed by the Chief Investigator or Co-investigator. The sponsor will undertake a review of the information. Events will be followed up until resolution, any appropriate further information will be sent by the research team in a timely manner.

The Manufacturer has a legal obligation to report all events that need to be reported to the Nominated Competent Authority immediately (without any unjustifiable delay) after a link is established between the event and the device, but no more than:

- 2 days following the awareness of the event for Serious Public Health Threat.
- 10 days following awareness of the event for Death or unanticipated serious deterioration in health.
- 30 days following the awareness of the event for all other event meeting the SAE criteria.

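### The eCRF window for pre-specified complications closes when the intervention ends, so it depends on arm and on weaning, and neither safety outcome alone compares the arms like with like

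*Protocol*

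**What the plan says.** Protocol section 6.1 lists catheter-placement and device complications and sets two rules for them.

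- **Channel:** "The events listed above must be entered onto the eCRF when appropriate as outcomes of interest, and therefore are exempt from SAE reporting".
- **Window:** "Pre-specified complications will be collected onto the eCRF for the duration of the trial intervention up to 28 days". The next sentence adds: "Any occurrence following this will be reported via the safety reporting process described in Section 7 of the CoReCCT Master Protocol".

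Section 4.4 gives one list of events that end the intervention, for NAVA and control alike. It includes day 28, successful unassisted breathing, death, an SAE related to the study intervention, and "NAVA equipment unavailable". Section 3.9, repeated in section 9, adds: "If a NAVA catheter is replaced by a non-NAVA catheter before 28 days based on clinical grounds this will be considered an intervention withdrawal".

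Section 3.4.2 names both "Serious adverse events up to hospital discharge" and the pre-specified complications among the secondary and safety outcomes. Section 6.3 states without exception: "All SAE/SADE/UADEs need to be reported via the CDMS to the trial team within one working day".

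**The concern.** The period over which listed complications are entered on the eCRF is set after randomisation. It closes at the event that defines the primary outcome, it can close because of harm, and some of its closing events can arise only in the NAVA arm. When it closes, the event changes both its reporting channel and, apparently, its threshold. During the intervention any listed event is recorded as an outcome of interest. Afterwards it goes to a safety process that section 6.1 describes, for events on neither list, as starting with an assessment of seriousness.

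Two consequences follow. First, the complication counts may differ between arms because the arms were observed for different lengths of time. Second, a serious listed event falls outside the SAE outcome or potentially inside it according to whether the intervention was still running. In an open-label trial whose device is a catheter, these are the safety comparisons that readers will look at first.

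**Working it through.** The protocol states no figure on this point, so there is none to reproduce. The check has three parts.

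**1. What closes the window, by arm**

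| Closing event | Source | Control | NAVA |
|---|---|---|---|
| Day 28 | 4.4, 6.1 | yes | yes |
| Successful unassisted breathing, or death (the primary-outcome events) | 4.4, 3.4.1 | yes | yes, sooner if NAVA works |
| Intervention-related SAE | 4.4 | nominally | yes |
| NAVA equipment unavailable | 4.4 | no practical meaning | yes |
| Replacement by a non-NAVA catheter | 3.9, 9 | cannot occur | yes, if withdrawal ends the intervention period |

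The rule is nominally common, but the realised window depends on allocation.

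**2. One event, two outcomes**

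Take a pneumothorax on day 12. In a control patient still ventilated it is a pre-specified complication, exempt from SAE reporting. In a NAVA patient whose intervention ended on day 10 because equipment was unavailable, it goes through the safety process as a potential SAE. A non-serious listed event on day 12, such as nasal bleeding, would be on the eCRF for the first patient and might be recorded nowhere for the second. Section 7 of the master protocol would settle that, and it is not at hand.

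**3. How far the windows could differ (illustration)**

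Inputs: control median 10 days and a 2-day reduction (section 8.1), hence 8 days for NAVA. Section 8.4 gives a hazard ratio of 1.25, which equals 10/8. Assumption: exponential durations. The window is the duration capped at 28 days, and its mean for median m is (m / ln 2) × (1 − 2^(−28/m)).

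- Control: (10 / 0.6931) × (1 − 2^(−2.8)) = 14.43 × (1 − 0.1436) = 12.36 days.
- NAVA: (8 / 0.6931) × (1 − 2^(−3.5)) = 11.54 × (1 − 0.0884) = 10.52 days.
- Ratio: 10.52 / 12.36 = 0.85.

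Other control medians, with either a 2-day reduction or a hazard ratio of 1.25:

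| Control median (days) | Ratio, 2-day reduction | Ratio, hazard ratio 1.25 |
|---|---|---|
| 6 | 0.69 | 0.82 |
| 7 | 0.75 | 0.83 |
| 10 | 0.85 | 0.85 |
| 14 | 0.92 | 0.88 |

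Next, suppose that a share p of NAVA patients also stop early for catheter or equipment reasons, at a time uniform over their own window. The protocol gives no value for p, so 5% to 20% is assumed. Those patients lose half their window on average, so the ratio is multiplied by (1 − p/2).

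| p | Ratio, 8 v 10 days | Ratio, equal durations |
|---|---|---|
| 0% | 0.85 | 1.00 |
| 5% | 0.83 | 0.98 |
| 10% | 0.81 | 0.95 |
| 20% | 0.77 | 0.90 |

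At an equal, constant daily risk, the expected eCRF counts would stand in these same ratios.

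**The case against.** The strongest reply is that the protocol loses little. Several stronger readings are tempting, and the documents do not support them.

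- *Complications after the intervention are not collected.* A reader might infer this from the window sentence alone. The next sentence sends them to the safety reporting process, and the data collection schedule in section 5.1 runs adverse events to hospital discharge in both arms. What changes is the channel. The possible gap is confined to later non-serious events.
- *The SAE outcome leaves out the harms NAVA could cause.* This is too broad. Only listed events during the intervention are exempt, and section 3.4.2 names them as safety endpoints in their own right. Unlisted events, and listed events after the window, still enter the safety process.
- *The arms have different windows by rule.* Section 4.4 gives one rule for both, and the divergence arises through its end criteria. Section 4.4 does not itself name catheter replacement, so reading the withdrawal in section 3.9 as closing the window is plausible but inferred.
- *NAVA will show 15% fewer complications, a bias in its favour.* The ratio of 0.85 assumes the full planned benefit and a constant daily risk. Some listed events belong to tube insertion. Others need an airway device in place, so less ventilated time is partly a real reduction in exposure. The direction also differs by outcome: early stopping can lower the NAVA complication count while raising its SAE count.
- *Serious device events lose the one-working-day route.* This is not established. Section 6.3 repeats no exemption, and the definitions and flowchart sit in the master protocol. The two sections are in tension, and the protocol does not resolve it.

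What stands against these replies is that the split between the two outcomes moves with allocation and weaning. Analysis cannot restore events that were never entered.

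**Conclusion.** The point holds in a limited form. The eCRF window for listed complications depends on allocation and on the primary outcome, so the same event can fall under either of two outcomes. Neither outcome alone compares the arms on equal terms.

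The size cannot be fixed from the protocol. The ratio of mean windows is 0.85 under the planning values. It ranges from 0.69 to 0.92 over control medians of 6 to 14 days, and is 1.00 with equal durations and no NAVA-only early stops. These ratios describe observation time. They do not estimate the number of events lost or the net bias. Whether later non-serious events go unrecorded depends on the master protocol.

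Separately, the exemption in section 6.1, the unqualified duty in section 6.3 and the intervention-related SAE criterion in section 4.4 do not fit together. It is unclear whether a serious listed catheter injury is an SAE for the purposes of the other two sections. The change is worth making but does not threaten the primary analysis.

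**What to change.** 1. In section 6.1, collect the listed complications in both arms over one fixed window from randomisation, for example to day 28 or hospital discharge, whichever is first, whatever the intervention status. Only death or discharge could then shorten it. A true reduction through less ventilated time would still show.
2. Record seriousness for each listed event on the eCRF.
3. Tabulate serious listed events together with SAEs by arm, alongside the separate complication endpoint.
4. Reconcile the exemption in section 6.1 with sections 6.3 and 4.4. State whether a serious listed event is subject to the one-working-day report, and whether it counts as an intervention-related SAE. That choice belongs to the sponsor and investigators.

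The cost is revised safety wording, a changed eCRF window with one added field, and slightly more event reporting by sites.

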6.2 EXPECTED EVENTS

SAEs which are considered possibly related, probably related or definitely related to the study intervention will be assessed for expectedness by the Sponsor. This expectedness assessment may be supported by items such as, but not limited to; associated domain working instructions; published literature; and the following list of events which details events previously documented in relation to the intervention.

6.3 REPORTING RESPONSIBILITIES SUMMARY

All SAE/SADE/UADEs need to be reported via the CDMS to the trial team within one working day of the investigator team becoming aware of them. Reports of related and unexpected SAEs should be submitted to ethics within 15 days of the Chief Investigator becoming aware of the event.

All reporting to the sponsor should as much information about the incident as possible and should be signed by the Chief Investigator or Co-investigator. The sponsor will undertake a review of the information. Events will be followed up until resolution, any appropriate further information will be sent by the research team in a timely manner.

The Manufacturer has a legal obligation to report all events that need to be reported to the Nominated Competent Authority immediately (without any unjustifiable delay) after a link is established between the event and the device, but no more than:

- 2 days following the awareness of the event for Serious Public Health Threat.
- 10 days following awareness of the event for Death or unanticipated serious deterioration in health.
- 30 days following the awareness of the event for all other event meeting the SAE criteria.

7 DATA MANAGEMENT

Full details on data management are provided in sections 6 and 10 of the CoReCCT master protocol.

7.1 DATA COLLECTION AND MANAGEMENT

Full details are listed in section 10 of the CoReCCT Master Protocol.

7.2 DATA SHARED WITH THIRD PARTIES

Full details are listed in section 12 of the CoReCCT Master Protocol.

7.3 ARCHIVING

Full details are listed in section 13 of the CoReCCT Master Protocol.

8 STATISTICS AND HEALTH ECONOMICS

8.1 SAMPLE SIZE CALCULATION

The trial will recruit a total of 900 (450 per arm) participants (using 90% power, 5% significance level, and 5% loss to follow-up) to detect effect size of 2-days reduction in duration of MV. The parameter estimates for this study have been derived as follows:

1. **Effect size of 2-days reduction:** Given previous meta-analyses [12-14] showed a reduction of MV duration with NAVA Technology of between 2.6 and 4.9 days, an effect size of 2 days is conservative and can be realistically achieved.
2. **Median duration of ventilation on the control arm:** Reported MV duration varies from 7 to 14 days in UK studies (i.e., 4.5 days- BREATHE study [32]; 14.1 days -OSCAR trial [33]). Amongst patients ventilated >48 hours (UK NAVA inclusion criteria), a commissioned report on 2018 and 2019 ICU admissions (ICNARC) and a recent, large international study [34] (Weansafe, Lancet Respiratory, May 2023) found median (IQR) MV durations of 6 days (4 to 11) and 7 days (4 to 12) respectively. To allow for any uncertainties and differences in the population, we have taken a more conservative estimate of 10 days for our sample size calculations.
3. **Loss to follow-up:** In the previous ICU studies, loss to follow-up ranges from 0% to 3% (1.1% - BREATHE [32]; 0% - OSCAR [33]; 0.4% - HARP-2 [35]; 3% - REST [36]). We have used a conservative estimate of 5% as our loss to follow-up rate.

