3.8 RANDOMISATION

Participants will be randomised via randomly permuted blocks using an automated web-based system on a one-to-one basis, stratified by site and prior randomisation to another CoReCCT trial, using a computer-generated randomisation schedule managed by the Warwick CTU. We have selected a parallel group RCT design to minimise selection bias and ensure against accidental bias.

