8.2 STATISTICAL ANALYSIS

The trial results will be reported in accordance with the Consolidated Standards of Reporting Trials (CONSORT). Primary analysis will be intention-to-treat. For our primary analysis, a cox-proportional hazard model will be used to estimate hazard ratio with 95% confidence interval (CI). If the proportional hazard assumption is not valid, we will run a sensitivity analysis by fitting a mixed effects partially proportional hazards regression model with censoring for deaths and loss to follow-up. Although death in ICU may be considered a competing event, censoring for deaths allows us to estimate the instantaneous risk of experiencing a successful extubation event at time t given that the patient is still alive at time t (known as “cause-specific hazard” of extubation for patients who have not yet died). Sites will be included in the model as a random effect, and treatment arm as a fixed effect. For secondary outcomes including quality-of-life measures which are continuous, mixed-effect linear regression models will be used to estimate the treatment effect with 95% CI. For secondary outcomes which are binary, mixed-effect logistic regression models will be used to estimate the treatment effect with 95% CI. We will explore different approaches that allow incorporation of multiple relevant outcomes including death into a single overall measure (e.g., win ratio [18]). A detailed statistical analysis plan will be agreed with the data monitoring committee.

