8.4 FUTILITY ANALYSES

The methods for futility analyses and determining futility boundaries which account for censored observations are very limited in the literature. Assuming there is no censoring (and for every patient, an event will be observed), we can use normal approximation methods for the log hazard ratio. This assumption is reasonable in the context of this study. In consultation with the DMC, we aim to plan for a futility analysis halfway through our trial (at 50% sample size). We will use the conventional conditional power boundaries at this interim point, where we will declare for futility if the conditional power is <15%. Assuming our hazard ratio is 1.25 (as per the sample size), this interim analysis (and boundaries) does not impact on the overall study power of 90%. This futility rule will be used as a guidance criterion by the DMC. The decision to stop will be based largely on clinical judgement of all the outcomes, as well as parameters that drive operational futility (recruitment).

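### The 90% power for 900 patients holds only if almost every followed patient has an event and the hazard ratio of 1.25 applies to that event, and the protocol defines the event in two incompatible ways

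*Protocol*

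**What the plan says.** Section 8.1 sets the size: "The trial will recruit a total of 900 (450 per arm) participants (using 90% power, 5% significance level, and 5% loss to follow-up". The planned effect is a cut of 2 days from a control median taken as 10 days. Loss to follow-up is the only attrition allowed for; death is not mentioned. Section 3.8 fixes allocation "on a one-to-one basis, stratified by site and prior randomisation to another CoReCCT trial".

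On the event itself:

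- Sections 1 and 3.4.1 end the primary outcome at first successful unassisted breathing or at death, so death is an endpoint.
- Section 8.4 agrees and takes the hazard ratio as 1.25: "Assuming there is no censoring (and for every patient, an event will be observed". It calls this reasonable for the study, and states that the futility look "does not impact on the overall study power of 90" per cent.
- Section 8.2 goes the other way. It describes a model that censors deaths and losses, and defends the choice: "Although death in ICU may be considered a competing event, censoring for deaths allows us to estimate" the cause-specific hazard of extubation among patients still alive. The model is introduced as a sensitivity analysis in case proportional hazards fails, but the justification is written in general terms.

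Below, weaning means first successful unassisted breathing.

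**The concern.** A patient who dies on the ventilator is an event under sections 1, 3.4.1 and 8.4 and a censored observation under section 8.2. These are different event counts and different hazard ratios, and one power statement cannot serve both without further assumptions. Because the sample size has almost no slack in events, the choice matters.

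The headline power, the smallest effect the trial can reliably detect, and the futility calculation all rest on it. If the analysis turns out to be the death-censored one, a null result could be read as a 90%-powered exclusion of a 2-day benefit when the true power was lower. If deaths are counted as events, the planned effect has to hold for a composite in which death counts the same as success, and the protocol does not say that 1.25 was chosen with that in mind.

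**Working it through.** **Inputs.** From section 8.1: N = 900, power 90%, significance 5%, loss 5%, control median 10 days, reduction 2 days. From section 3.8: 1:1 allocation. From section 8.4: hazard ratio (HR) 1.25. The share of patients dying before weaning is not given, so it is an assumption, p, shown over a range.

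**Reproducing 900.** With exponential times, HR = 10/8 = 1.25, as section 8.4 says.

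- Schoenfeld: events = 4 × (1.960 + 1.282)² / (ln 1.25)² = 844; 844/0.95 = 889.
- Freedman: 852 events; 852/0.95 = 897.

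Both round to 900 with a two-sided test. One-sided versions give 725 and 731 and do not reproduce it. The arithmetic is therefore sound on its own assumptions.

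**Slack.** Followed patients: 900 × 0.95 = 855. Power with 855 events is Φ(√855/2 × ln 1.25 − 1.96) = 90.4%. The margin is 855 − 844 = 11 patients, or 11/855 = 1.3%.

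**Deaths censored.** Events d = 855 × (1 − p); power = Φ(√d/2 × ln 1.25 − 1.96).

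**Deaths as events, HR 1.25 on weaning only, death hazard equal between arms.** With constant hazards, composite HR = (1 − p) × 1.25 + p × 1.0, and d = 855.

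| Assumed p | Events, deaths censored | Power, deaths censored | Composite HR | Power, deaths as events |
|---|---|---|---|---|
| 0% | 855 | 90.4% | 1.25 | 90.4% |
| 5% | 812 | 88.9% | 1.238 | 87.6% |
| 10% | 770 | 87.2% | 1.225 | 84.3% |
| 20% | 684 | 83.1% | 1.20 | 76.0% |
| 25% | 641 | 80.7% | 1.19 | 71.0% |
| 30% | 598 | 77.9% | 1.175 | 65.5% |
| 40% | 513 | 71.5% | 1.15 | 53.3% |

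A simulation with exponential times (2,000 runs, 855 patients, no time limit) gave 84%, 82% and 78% at 20, 25 and 30% deaths with deaths censored, in line with the formula.

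**Detectable HR at 90% power, deaths censored.** exp(2 × 3.242/√d) = 1.28, 1.29 and 1.30 at 20, 25 and 30% deaths.

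**Deaths as events, HR 1.25 on the composite itself.** Power is 90.4% at any p. If death is unaffected, the weaning HR that this implies is (1.25 − p)/(1 − p) = 1.31, 1.33 and 1.36 at 20, 25 and 30% deaths.

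**Futility.** With 844 events and conditional power computed at HR 1.25, a 15% rule at half the information leaves power at 90.0%. The rule itself costs almost nothing on that reading. The weak part is the 90% it starts from.

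**The case against.** The strongest reply is that the protocol defines its outcome to end at death, so each followed patient does have an event, section 8.4 follows from sections 1 and 3.4.1, and 900 gives 90.4%. On that reading, section 8.2 censors deaths only in a sensitivity model. This is a fair reading, and if HR 1.25 was meant for the composite the stated power stands. But section 8.2 then justifies the cause-specific hazard without limiting it to the sensitivity model, and nothing says which event the 1.25 refers to.

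A reader might infer that the trial simply has 78 to 83% power. The documents do not support that: it takes both the death-censored analysis and a 20 to 30% death share, and no rate is given. Section 3.5.2 also excludes patients whose death is imminent within 48 hours.

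A reader might also infer that counting deaths cannot restore the power because a composite HR of 1.25 would need NAVA to hasten death. That does not follow either. A weaning HR of 1.31 to 1.36 with no effect on death is enough at 20 to 30% deaths, and the pooled reduction of 2.64 days in section 2.2, set against a 10-day median, corresponds to about 10/7.36 = 1.36.

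Finally, the 10-day median is deliberately cautious. Section 8.1 cites medians of 6 and 7 days in patients ventilated for more than 48 hours. A 2-day reduction from 7 days is HR 7/5 = 1.4; at 30% deaths, power is then about 98% with deaths censored, or about 95% with deaths as events and unaffected (composite HR 0.7 × 1.4 + 0.3 = 1.28). This is real reassurance, but it concerns another design point. The stated 90%, and the futility claim, are for HR 1.25.

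**Conclusion.** The calculation of 900 is correct for its assumptions, but those assumptions are not consistent with everything the protocol says about deaths. The 90% requires about 844 events from 855 followed patients and a hazard ratio of 1.25 on that same event.

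- If deaths are censored, power at HR 1.25 falls below 90% once more than about 1% die before weaning, and lies between 88.9% and 77.9% for an assumed 5 to 30%.
- If deaths are events, power is 90.4% when 1.25 refers to the composite, and about 76%, 71% and 65% at 20, 25 and 30% deaths when it refers to weaning only and death is unaffected. It would be lower still if NAVA reduced deaths, since the composite scores death like success; section 2.3 reports a pilot relative risk of 0.5 for in-hospital death, from a small trial.

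The contradiction and the missing mortality assumption are certain from the text. The size of any shortfall depends on a death share that the protocol does not give, on constant hazards for the composite figures, and on which event definition is adopted. A later analysis plan can choose the definition, but it cannot make sections 8.1 and 8.4 agree with that choice.

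**What to change.** Name one event definition for the primary Cox model and use it in sections 8.1, 8.2 and 8.4. State an assumed proportion dying before weaning, with a range, and from 900 patients give the expected events and either the resulting power or the hazard ratio detectable with 90% power.

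- *If deaths are censored:* reconcile this with the outcome wording in sections 1 and 3.4.1, remove the no-censoring assumption from section 8.4, place the futility look at 50% of expected events (for example 641/2, about 320, if 25% die first), and recompute the conditional power and the claim about overall power.
- *If deaths are events:* say that HR 1.25 refers to the composite, state the weaning effect it implies (about 1.31 to 1.36 at 20 to 30% deaths with no effect on death), and confine the censoring text in section 8.2 explicitly to the sensitivity analysis.

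The cost is wording and recalculation. No extra patients are needed, provided the sponsor accepts that the stated power may be less favourable. For scale, holding 90% with deaths censored would take 1,112, 1,186 or 1,271 patients at 20, 25 or 30% deaths (845 events divided by 0.95 and by 1 − p).
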